9.3 Primary Efficacy Endpoint and Analyses

9.3.1 Primary Efficacy Endpoint

The primary endpoint is the proportion of subjects achieving sustained remission at Week 52. Sustained remission is defined as having achieved both of the following:

[figure not shown]
- Absence of GCA signs and symptoms from Week 12 through Week 52
- Adherence to the protocol-defined CS taper regimen.

Subject who belongs to any one of following categories will be considered as not adhering to the protocol-defined taper regimen:

- Investigator-initiated escape therapy in any time in Period 1
- Received more than 100 mg (prednisone-equivalent dose) additional systemic CS for GCA indication during Period 1 of the study, without being identified as escape therapy. Additional systemic CS is defined as any systemic CS captured as concomitant medication other than IRT dispensed CS for taper.

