5.3 Prohibited Medications and Therapy

Biologic Therapies

Subjects must have discontinued any biologic therapies with immunosuppressive potential prior to the first dose of study drug as specified in the washout procedures (Eligibility Criterion 23, Section 5.1). For all other biologic therapies, contact the AbbVie Therapeutic Area Medical Director (TA MD) for the washout period required prior to the first dose of study drug.

Biologic therapies with immunosuppressive potential are prohibited medications through the end of study drug administration, and include, but are not limited to, the following:

- Abatacept
- Adalimumab
- Anakinra
- Anifrolumab
- Belimumab
- Certolizumab
- Dupilumab
- Etanercept
- Golimumab
- Guselkumab
- Infliximab
- Ixekizumab
- Lebrikizumab
- Natalizumab

- Nemolizumab
- Rituximab
- Risankizumab
- Sarilumab
- Secukinumab
- Tocilizumab
- Tralokinumab
- Ustekinumab
- Vedolizumab

Immunosuppressants

Introduction of additional systemic immunosuppressants (such as methotrexate, hydroxychloroquine, cyclosporine, azathioprine, or mycophenolate) concurrent with study drug is prohibited from 4 weeks prior to first dose of study drug through the end of the study. Subjects who discontinue study drug may receive treatment with immunosuppressants in accordance with the investigator's best clinical judgment, irrespective of whether or not the subject decides to continue participation in the study.

Parenteral Corticosteroids

Intra-articular, trigger-point/tender point injection, intra-bursa, or epidural administration of CS is not permitted during Period 1 of the study. Section 5.4 describes use of CS for non-GCA-related conditions that is allowed during the study. During Period 2 of the study, one intra-articular, trigger-point/tender point injection, intra-bursal injection, epidural, or intra-muscular injection is allowed for non-GCA-related conditions if it meets the permitted amount of CS allowed in Period 2 as described in Section 5.4.

Strong CYP3A Inhibitors or Inducers

Systemic use of known strong CYP3A inhibitors is prohibited from Screening through the end of the study and strong CYP3A inducers are prohibited from 30 days prior to study drug administration through the end of the study. Commonly used strong CYP3A inhibitors and inducers are listed in Table 1. In addition, herbal therapies and other traditional medicines with unknown effects on CYP3A are not permitted from Screening through the end of study drug administration.

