5.4 Prior and Concomitant Therapy

Any medication or vaccine (including over the counter or prescription medicines, vitamins and/or herbal supplements) that the subject is receiving within 30 days prior to Screening and/or receives during the study must be recorded along with the reason for use, date(s) of administration including start and end dates, and dosage information including dose, route and frequency must be recorded in the eCRF. Also, medications taken for GCA since date of diagnosis (based on subject recollection and available medical records) should be entered into the appropriate eCRF inclusive of the dates of first and last dose, maximum dosage taken, route of administration and reason for discontinuation, if known.

Subjects must be consented for the study prior to discontinuing any prohibited medications for the purpose of meeting study eligibility.

Throughout the study, addition of a biologic or non-biologic immunomodulators other than CS while taking blinded study drug (upadacitinib or PBO) is not permitted for rescue.

Inhaled and nasal CS for stable medical conditions are allowed during the study but must have been at a stable dose for \geq 4 weeks prior to the Baseline Visit. Short-term use (\leq 10 days) of CS (oral, inhaled, nasal, intravenous, or intramuscular) for non-GCA-related conditions for events such as exacerbation of asthma or chronic obstructive pulmonary disease, allergic reactions, or serious infection when additional CS may be required to prevent adrenal insufficiency (a total of up to 100 mg of prednisone or equivalent

through 52 weeks in Period 1 and a total of up to 100 mg of prednisone or equivalent through 52 weeks in Period 2) is allowed during the study.

Subjects should be treated with anti-platelet therapy (aspirin or clopidogrel) at the discretion of the investigator and in accordance with local standard-of-care practice.

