5.5 Discontinuation from Study Drug or Subject Withdrawal from Study

Subjects can request to be discontinued from participating in the study at any time for any reason including but not limited to disease progression or lack of response to treatment. The investigator may discontinue any subject's participation at any time for any reason, including but not limited to disease progression, lack of response to treatment, an AE, safety concerns, or failure to comply with the protocol.

Subjects will have study drug discontinued immediately if any of the following occur:

- Abnormal laboratory results or AEs that either meet the criteria of discontinuation of study drug, as stated in Section 6.2 or rule out safe continuation of study drug.
- Serious infection (e.g., sepsis) that cannot be adequately controlled by anti-infective treatment or would put the subject at risk for continued participation in the trial as determined by the investigator.
- Confirmed diagnosis of deep vein thrombosis, pulmonary embolus or noncardiac, non-neurologic arterial thrombosis.
- The investigator believes it is in the best interest of the subject.
- The subject requests withdrawal from the study.
- Inclusion or exclusion criteria violation was noted after the subject started the study drug, when continuation of the study drug would place the subject at risk.
- Introduction of prohibited medications or dosages when continuation of the study drug would place the subject at risk.
- Subject is non-compliant with TB prophylaxis (if applicable) or develops active TB at any time during the study.
- The subject becomes pregnant while on study drug.

- Any malignancy, except for a localized nonmelanoma skin cancer (NMSC) or a carcinoma in-situ of the cervix which can successfully be treated at its localization.
- The investigator determines the subject is significantly non-compliant with study procedures.
- Subject develops a gastrointestinal perforation (other than due to appendicitis or mechanical injury).
- The subject experiences a serious hypersensitivity reaction without an alternative etiology.
- At Week 52, subject does not meet criteria for continuation into Period 2.

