7.3 Protocol Deviations

Protocol deviations include eligibility criteria violations, receipt of wrong treatment or incorrect dose of study treatment, development of withdrawal criteria without being withdrawn, and use of prohibited concomitant medications.

For each of the following protocol deviation categories and across all categories, the number and percentage of randomized subjects with at least one protocol deviation will be summarized overall and by treatment group:

- Subject entered into the study even though did not satisfy entry criteria;
- Subject developed withdrawal criteria during the study but was not withdrawn;
- Subject received wrong treatment or incorrect dose of study treatment;
- Subject took prohibited concomitant medication.

8.0 Handling of Potential Intercurrent Events for the Primary and Multiplicity-Controlled Secondary Endpoints

The primary endpoint and multiplicity-controlled secondary endpoints (defined in Section 3.1 and Section 3.2) will be analyzed based on FAS1, except for the endpoint of the rate of CS-related AEs which will be analyzed based on SS1.

[figure not shown]
Intercurrent Events (ICEs):

- ICE1: Premature discontinuation from study treatment
- ICE2: Investigator-initiated CS escape therapy
- ICE3: Received more than 100 mg prednisone (or equivalent) systemic CS for a non-GCA indication

The following method will be used to address potential intercurrent events above:

For the primary analysis of the primary efficacy endpoint, estimand with composite and hypothetical strategy will be used. For ICE1: subjects will be considered as non-responders after ICE1. ICE2 is not applicable for the primary endpoint. For ICE3: data after ICE3 will be handled by multiple imputation (MI).

For the primary analysis of the multiplicity-controlled secondary binary remission related efficacy endpoints, estimands with composite and hypothetical strategy will be used. For

ICE1: subjects will be considered as non-responders after ICE1. ICE2 is not applicable for remission related endpoints. For ICE3: data after ICE3 will be handled by MI.

For the primary analysis of the secondary binary efficacy endpoint of proportion of subjects who experience at least 1 disease flare through Week 52, estimand with treatment policy strategy to handle ICEs will be used: data collected will be used regardless of ICE1 or ICE3. ICE2 is not applicable for the endpoint of proportion of subjects who experience at least 1 disease flare.

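### No intercurrent event or adherence rule covers a prohibited biologic, JAK inhibitor or immunosuppressant started on study drug, so such a subject can still count as a remission responder

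*SAP*

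**What the plan says.** SAP 9.3.1 builds sustained remission (V0 in SAP Table 3) from two components: "Absence of GCA signs and symptoms from Week 12 through Week 52", and adherence to the CS taper. Failure of adherence is defined by a closed list: "Subject who belongs to any one of following categories will be considered as not adhering to the protocol-defined taper regimen". The list has two entries: "Investigator-initiated escape therapy in any time in Period 1", and "Received more than 100 mg (prednisone-equivalent dose) additional systemic CS for GCA indication during Period 1 of the study" where this was not identified as escape. SAP 9.4.1 applies the same list to V1 and V5, and a version cut at Week 24 to V6.

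SAP 8.0 names three intercurrent events. ICE1 is stopping study treatment (composite, non-responder). ICE2 is CS escape, stated as not applicable to remission endpoints. The third reads "ICE3: Received more than 100 mg prednisone (or equivalent) systemic CS for a non-GCA indication" and is handled by multiple imputation.

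Protocol 5.3 prohibits immunosuppressive biologics, JAK inhibitors and added systemic immunosuppressants during study treatment. Protocol 5.4 adds that "addition of a biologic or non-biologic immunomodulators other than CS while taking blinded study drug (upadacitinib or PBO) is not permitted for rescue". On local steroids, Protocol 5.3 says: "Intra-articular, trigger-point/tender point injection, intra-bursa, or epidural administration of CS is not permitted during Period 1 of the study". Protocol 5.5 lists, among the reasons for immediate study drug stop, "Introduction of prohibited medications or dosages when continuation of the study drug would place the subject at risk".

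SAP 7.3 tabulates prohibited medication as a deviation. SAP 4.0 and 9.3.3 use the Per-Protocol set only for a supplementary analysis of the primary endpoint.

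**The concern.** The documents foresee non-CS rescue on blinded drug and forbid it, but the primary analysis attaches no consequence to it. The handling is then uneven. A subject who stops study drug and takes tocilizumab is a non-responder through ICE1. A subject who takes it without stopping, which is the larger departure from the protocol, meets no intercurrent event. Likewise CS escape at Week 8 fails V0, while methotrexate at Week 8 for the same symptoms need not.

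At stake is whether V0, V1, V5 and V6 can credit the randomised arm with a remission obtained on a treatment that was not assigned. There is also a procedural cost: with no rule in place, how to classify such a subject becomes a decision made when the case is found.

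**Working it through.** **Step 1. Coverage.** Each treatment is set against all five rules, for a subject who stays on study drug and has no CS escape.

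| Rule | Biologic or JAK inhibitor | Systemic immunosuppressant | Local CS injection |
|---|---|---|---|
| ICE1, study treatment stop (SAP 8.0) | no | no | no |
| ICE2, CS escape (SAP 8.0) | no | no | no |
| ICE3, systemic CS, non-GCA (SAP 8.0) | no | no | no |
| Adherence: escape therapy (SAP 9.3.1) | no | no | no |
| Adherence: over 100 mg systemic CS for GCA (SAP 9.3.1) | no | no | no |

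SAP 9.3.1 writes escape therapy without naming CS, but SAP 8.0 (ICE2) and Protocol 5.8 both describe escape as corticosteroid, and 5.8 specifies open-label prednisone or prednisolone. Protocol 5.1, criterion 24, glosses systemic CS as oral, intravenous or intramuscular, so a bursal or intra-articular injection falls outside. Result: 0 of 5 rules in each column.

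**Step 2. Can the subject stay on study drug?** Protocol 5.8 sends a subject who flares or cannot follow the taper to open-label CS escape. If other treatment is judged necessary after 2 weeks, study drug is stopped. Both steps give non-response. Reaching the gap therefore means leaving this route: escape is not used and a prohibited agent is given on blinded drug. Once that happens, the prohibited-medication clause of Protocol 5.5 compels a stop only if continuing is a risk, so ICE1 does not follow automatically.

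**Step 3. Which endpoints can then be met?**
- V0 needs no recorded GCA signs from Week 12 through Week 52. It can be met if the agent was started before Week 12, for a raised ESR alone (ESR is not part of V0, and under Protocol 5.7 the Laboratory Assessor reports raised values to the investigator), or for symptoms that came and went between visits. Visits are 8 weeks apart from Week 28 to Week 52 (Protocol Appendix D).
- V1 adds ESR and hsCRP over the same window, so a recorded ESR elevation attributed to GCA also fails it.
- V5 and V6 judge signs, ESR and hsCRP at Week 52 and Week 24 only. A subject with signs recorded at Week 36, then given a prohibited biologic on study drug without CS escape, fails V0 and V1 but can be a V5 responder.

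**Step 4. Size.** Inputs: 210 subjects on 15 mg and 105 on placebo (Protocol 4.1); 60% versus 40%, Fisher's exact test, two-sided 0.05, at least 90% power (SAP 2.4). Full enumeration gives 91.0%, so the stated power reproduces.

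One misclassified subject moves an arm's rate by 1/n:
- placebo: 1/105 = 0.95 points;
- 15 mg: 1/210 = 0.48 points.

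The documents give no frequency, so the shares below are assumptions. Take 60% and 40% as the rates counted under the current rules and recode a share m15 or mP of each arm to non-response. The difference becomes (0.60 − m15) − (0.40 − mP).

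| Share recoded | Difference (points) | Fisher power |
|---|---|---|
| none | 20 | 91.0% |
| 15 mg only: 1% / 2% / 3% / 5% | 19 / 18 / 17 / 15 | 87.9% / 84.1% / 79.6% / 68.7% |
| same share in both arms, 1% to 5% | 20 | 91.0% to 91.2% |
| placebo only: 2% / 5% | 22 / 25 | 95.4% / 98.7% |

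**The case against.** A reader might infer that any subject given prohibited rescue on study drug is automatically a sustained-remission responder. The documents do not support that. Signs are assessed at every visit (Protocol 5.7), and procedures may also be done at unscheduled visits (Protocol Appendix D, Note 1). Any GCA sign recorded from Week 12 through Week 52 fails V0 and V1 whatever treatment followed. Rescue prompted by returning symptoms in that window will often be caught this way.

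Nor do the documents permit such rescue. Protocol 5.8 leads through CS escape to study drug stop, and Protocol 5.5 separately requires a stop when the investigator finds significant non-compliance. The case is a deviation and may be rare. It is tabulated under SAP 7.3 and might be removed from the Per-Protocol set, whose criteria are to be fixed before lock.

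It is also fair that failing a subject for any local injection would be harsher than the plan is on systemic CS for GCA, where up to 100 mg outside escape leaves adherence intact.

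These points limit the concern without removing it. The routes in Step 3 stay open, and V5 and V6 lack the window-long symptom check. The Per-Protocol analysis is specified only for the primary endpoint, and it drops the subject instead of counting a failure. The point about injections stands and shapes the fix.

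**Conclusion.** The gap is real and narrow. Under the written rules, a subject who starts a prohibited biologic, JAK inhibitor or systemic immunosuppressant in Period 1 and remains on study drug can be counted as a responder, most readily for V5 and V6. This rests on a protocol deviation having occurred and on no CS escape having been given.

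The size is 0.95 points per placebo subject or 0.48 points per 15 mg subject, at planned arm sizes. The total is unknown because no frequency is given. The direction is unknown too: misclassification in placebo narrows the observed difference, misclassification in the 15 mg arm widens it, and equal shares leave it unchanged. A reader might infer a bias in favour of upadacitinib, or an expected shift of a given number of points; the documents support neither. The rows in Step 4 illustrate sensitivity and do not forecast. This is a cheap improvement to the estimand and does not challenge the design or the stated power.

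**What to change.** 1. In SAP 8.0, Table 1 and the remission-related row of Table 2, add an intercurrent event: start, while on study drug in Period 1, of a biologic, JAK inhibitor or systemic immunosuppressant prohibited by the protocol. Handle it by the composite strategy, non-responder from that date, as for ICE1.
2. Identify cases blind to treatment from the concomitant medication eCRF before database lock. Protocol 5.4 already requires reason, dates and dose to be recorded.
3. For local CS injections given for GCA or PMR signs, count the prednisone-equivalent dose toward the existing 100 mg GCA rule in SAP 9.3.1, with matching wording in 9.4.1. This treats them on the same footing as systemic CS and does not fail a subject for any single injection.

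The cost is SAP wording and one derivation, with no new data and no change to clinical conduct. The downside is that a few subjects become non-responders, so response rates may be slightly lower.

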9.3.2 Main Analysis of Primary Efficacy Endpoint

The statistical null hypothesis corresponding to the primary endpoint is that there is no difference between either upadacitinib 15mg QD or 7.5mg QD in combination with a 26-week CS taper regimen group and the placebo in combination with a 52-week CS taper regimen group in terms of the proportion of subjects achieving sustained remission at Week 52 in Period 1.

Analysis of the primary endpoint will be conducted on the FAS1 based on treatment as randomized. Comparison will be made between each upadacitinib group and placebo group using the Cochran-Mantel-Haenszel (CMH) test for common risk difference estimated by a weighted average of risk difference across strata using the Mantel-Haenszel weights. The strata include stratification factors (Baseline CS dose [prednisone or prednisolone > 30 mg, prednisone or prednisolone ≤ 30 mg], and Baseline disease status [new onset disease, relapsing disease]). NRI-MI will be the primary approach in handling missing values. Point estimate, p-value, and 95% CIs for the difference in proportions between each upadacitinib group and placebo group will be provided.

The attributes of the estimand corresponding to the primary efficacy endpoint are summarized in Table 1.

Table 1. Summary of the Estimand Attributes Corresponding to the Primary Efficacy Endpoint

	Attributes of the Estimand					
Estimand Label	Treatment	Endpoint	Population	Handling of Intercurrent Events	Statistical Summary	
Primary	Upadacitinib vs. Placebo	Achievement of sustained remission at Week 52	Subjects with GCA	 ICE1: composite Subjects will be considered as non-responders after ICE1. ICE3: hypothetical Data after ICE3 will be imputed by MI. 	Difference in proportion of subjects achieving sustained remission at Week 52	

9.3.3 Sensitivity and Supplementary Analyses of the Primary Efficacy Endpoint

[figure not shown]
The same primary efficacy analysis will also be performed on Per-Protocol Analysis Set as a supplementary analysis for the primary efficacy endpoint.

9.4 Secondary Efficacy Endpoints and Analyses

9.4.1 Multiplicity-Controlled Secondary Efficacy Endpoints

The multiplicity-controlled secondary endpoints are:

- 1. Proportion of subjects achieving sustained complete remission from Week 12 through Week 52. Sustained complete remission is defined as having achieved all of the following:
 - Absence of GCA signs and symptoms from Week 12 through Week 52;
 - Normalization of ESR (to \leq 30 mm/hr; if ESR > 30 mm/hr and elevation is not attributable to GCA, this criterion can still be met) from Week 12 through Week 52;
 - Normalization of hsCRP (to < 1 mg/dL without elevation [on 2 consecutive visits] to ≥ 1 mg/dL) from Week 12 through Week 52; and
 - Adherence to the protocol-defined CS taper regimen.
- 2. Cumulative CS exposure through Week 52.
- 3. Time to first disease flare through Week 52. Disease flare is defined as an event determined by the investigator to represent recurrence of GCA signs or symptoms or an ESR measurement > 30 mm/hr (attributable to GCA) AND requiring an increase in CS dose.
- 4. Proportion of subjects who experience at least 1 disease flare through Week 52.
- 5. Proportion of subjects in complete remission at Week 52. Complete remission is defined as having achieved all of the following:
 - Absence of GCA signs and symptoms;
 - Normalization of ESR (to \leq 30 mm/hr); if ESR \geq 30 mm/hr and elevation is not attributable to GCA, this criterion can still be met.
 - Normalization of hsCRP to < 1 mg/dL; and
 - Adherence to the protocol-defined CS taper regimen.
- 6. Proportion of subjects in complete remission at Week 24.
- 7. Change from Baseline in the 36-item Short Form Quality of Life Questionnaire (SF-36) Physical Component Score (PCS) at Week 52.
- 8. A group of four endpoints:
 - Number of disease flares per subject through Week 52;
 - Change from Baseline in Functional Assessment of Chronic Illness Therapy-Fatigue (FACIT-Fatigue) at Week 52;
 - Assessment of Treatment Satisfaction Questionnaire for Medication (TSQM) patient global satisfaction subscale at Week 52;
 - Rate of CS-related AEs* through Week 52
- * CS related AE is defined as treatment emergent adverse events related to prednisone/prednisolone (or matching placebo) according to the investigator.

For remission-related secondary endpoints (except for the endpoint of complete remission at Week 24), a subject who belongs to any one of following categories will be considered as not adhering to the protocol-defined CS taper regimen:

- Investigator-initiated escape therapy at any time in Period 1
- Received more than 100 mg (prednisone-equivalent dose) additional systemic CS for GCA indication during Period 1 of the study, without being identified as escape therapy. Any additional systemic CS is defined as any systemic CS administered as a concomitant medication other than the IRT dispensed CS for taper.

For the endpoint of complete remission at Week 24, a subject who belongs to any one of following categories will be considered as not adhering to the protocol-defined CS taper regimen:

- Investigator-initiated escape therapy up to Week 24
- Received more than 100 mg (prednisone-equivalent dose) of additional systemic CS for GCA indication up to Week 24.

[figure not shown]
Disease flare is considered only after an assessment meets all the 3 following criteria:

- Absence of recurrence of GCA signs and symptoms
- Normalization of ESR
- No CS dose increase

For the endpoints of disease flare, an increase in CS dose is defined as:

- Investigator-initiated escape therapy in Period 1
- Received additional GCA-related systemic CS dose(s) in Period 1

For the endpoint of number of disease flares per subject through Week 52, all flares occurred through Week 52 will be counted.

[figure not shown]
